We will include the below text in secure emails or via Partners Patient Gateway, so that patients will have the ability to opt-out:

"The Mass General Brigham (MGB) standard is to send email securely. This requires you to initially set up and activate an account with a password. You can then use the password to access secure emails sent to you from MGB. If you prefer, we can send you "unencrypted" email that is not secure and could result in the unauthorized use or disclosure of your information. If you want to receive communications by unencrypted email despite these risks, MGB will not be held responsible. Your preference to receive unencrypted email will apply to:

for research: [emails sent to you from research staff in this study. If you wish to communicate with other research staff at MGB regarding additional studies, your preference will have to be documented with each research group.]

for clinicians: [emails sent from clinicians and staff at this practice or department.]

for finance: [emails sent to you from Patient Billing Solutions and the Patient Service Center.]

Please confirm receipt of this email and indicate if your preference is to NOT receive secure emails from me at this time. If I do not hear back from you, then all future emails will be sent either via patient gateway or via secure messaging as is MGB policy."

Detailed Protocol – Reinforcement Learning in Diabetes Mellitus Trial

PI: [name]

Version 5. April 1 2021

Patients who prefer to correspond via email and to complete surveys electronically, will have the option to do so securely via the above channels for email and via REDCap, with all links sent securely as well.

Study Procedures

Participants have two study-related visits. These study visits can be completed virtually or in-person during clinic visits (if/when COVID-19 precautions are lifted) and both sets of procedures are described in further detail below.

Using a random number generator using stratification by baseline self-reported adherence and HbA1c control, the study research assistant will randomize 30 patients to the reinforcement learning arm and 30 patients to usual care. Other clinic staff and analysts will be blinded to arm assignment.

Virtual Study Procedures

1st Virtual Study Visit

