Subjects will provide written informed consent for all study procedures, including the use of text messages, and be enrolled at Brigham and Women's Hospital. The study staff will conduct the consent discussion via video and obtain paperless consent or e-consent from the participant through the MGB approved REDCap e-consent platform. After this visit, they will be mailed an electronic pill bottle manufactured by Pillsy along with written instructions for setup (see Attachments), which participants will be asked to use for the duration of the study. Based on data from prior trials, poorly-controlled patients with type 2 diabetes take an average of two oral glucose-lowering medications, and we expect to distribute approximately two EDMs per patient but no more than three.

At the baseline visit, we will also collect some basic information from subjects to administratively manage the study: name, address, email address, telephone number and the best times and days to contact, in addition to sociodemographic information (see demographics baseline questionnaire). For the patient to complete the surveys in the REDCap database, we will provide them with a secure link to the online database so they can complete the surveys at their convenience. The survey invites will be sent via secure email or SMS using the Twilio platform, a third-party web service integrated into REDCap, which will provide the participant with the survey URL, depending on patient preference. We will review contact information with subjects at each study visit to make sure that we have the most accurate information. Contact information will be stored in the password-protected REDCap database.

Additional information on demographics, diagnoses, medications, comorbidities, laboratory tests and disease activity will be abstracted from participants' medical records. Data will be collected through chart review as well as RPDR and entered into our REDCap database.

Before beginning follow-up, subjects in both arms will be contacted within 2 business days to review procedures, confirm the functionality of their bottles, and verify cellphone numbers for delivery of the intervention.

Detailed Protocol – Reinforcement Learning in Diabetes Mellitus Trial

PI: [name]

Version 5. April 1 2021

Optional Check-in

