Participants will receive their Pillsy electronic pill bottle in the mail along with written instructions on how to setup and use of the Pillsy bottle. They will also be provided with contact information for assistance from the study staff to properly setup their electronic pill bottle. The Pillsy bottle works as a standard pill bottle in which participants will store their medications. To ensure that real-time data is transmitted to the Pillsy server, participants will also download the Pillsy mobile application on their phone that will be connected by Bluetooth to their electronic pill bottle. Participants will not otherwise be asked to engage with the mobile application. Before beginning follow-up, subjects in both arms will be contacted to review procedures, confirm the functionality of their bottles, and verify cellphone numbers for delivery of the intervention.

Trial Period

Participants will be asked to use the electronic pill bottle for 6 months. As participants receive medication refills, they will transfer their pills to the Pillsy electronic pill bottle. Throughout the study, participant medication use data will be captured by the electronic pill bottles. The Pillsy electronic pill bottles employ electronic date/time stamp technology that is triggered by opening the pill bottle. Dates and times of bottle opening (and therefore adherence) are transmitted by Bluetooth to the patient's phone through the Pillsy mobile application.

The mobile application data will be automatically transferred to a secure, password-protected Pillsy portal hosted on a secure server located outside of BWH. These uploaded data will be de-identified, except for bottle opening dates and times. Participants will be assigned a study-specific ID, and the electronic bottles will only be linked to this participant by the study-specific ID. These data will only be accessible to the MGB researchers with password-protected access to the Pillsy portal. The only potentially identifiable data in the Pillsy portal are bottle opening dates, times, and study-specific ID.

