Patients in the reinforcement learning arm will receive text messages based on their EDM-measured adherence. Based on patient's fixed characteristics and time-varying responses to the messages, the algorithm will determine which text message to send and adapt over time to the messages that individual patients most respond to. The learning algorithm will be re-run daily based on recent adherence patterns and will deliver text messages based on those patterns. Patients in the usual care arm may receive up to daily, untailored text messages.

Patients in both arms may receive disconnectedness text messages, spaced three days apart, if their pill bottles become disconnected from their Pillsy mobile application for longer than a week. Study staff may call patients up to two times, spaced two weeks apart, if their pill bottles become disconnected from their Pillsy mobile application for longer than two weeks. If patients remain disconnected for the rest of the study period, study staff may call patients to reconnect their pill bottles at the end of the study.

Detailed Protocol – Reinforcement Learning in Diabetes Mellitus Trial

PI: [name]

Version 5. April 1 2021

The reinforcement learning algorithm will be periodically updated by sending completely de-identified modeling data to a Microsoft server. No patient identifiers will be included in any data on the Microsoft Azure server, only study-specific ID. This server will only be accessible by study staff. To update the reinforcement learning prediction model, study staff will manually upload and download data from the algorithm from the server. To do so, first, study staff will create a spreadsheet with 7-day adherence data from the Pillsy portal onto a MGB computer. This spreadsheet will include EDM-measured adherence as binary indicators (yes/no) for the past 7 days (i.e., dates/times will be removed). Then, study staff will upload this spreadsheet into the reinforcement learning algorithm model. The algorithm will then send fully de-identified data back to the MGB server with its updated prediction information about which type of text to send for each intervention subject. Study staff will then log onto the secure text messaging vendor system already used by MGB to schedule the correct text for each participant for the next day.

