Before beginning follow-up, subjects in both arms will be contacted within 2 business days to review procedures, confirm the functionality of their bottles, and verify cellphone numbers for delivery of the intervention.

[figure not shown]
Trial Period

The trial period protocol for the in-person study participants is exactly the same as the protocol for the virtual study participants described above.

2nd Study Visit

At the 2nd study visit, participants will be offered a \$50 Amazon gift card, and they will be able to keep their Pillsy EDM device(s) for personal use. Participants will also be asked to complete a questionnaire about their self-reported medication use and adherence and perspectives on the intervention (if applicable) or EDM monitors.

Study Schema

Outcomes

The trial's primary outcome is medication adherence assessed in the 6 months after randomization. Medication adherence will be measured by averaging daily adherence (as described above) for each medication across each patient beginning the day after randomization until 180 days after randomization. Secondary outcomes include change in glycemic control as assessed using HbA1c, and self-reported adherence at the end of follow-up. HbA1c values will be collected from routine measurements recorded in the EHR system; we will use the value closest to each patient's 6-month end of follow-up, up to 1 month after

Detailed Protocol – Reinforcement Learning in Diabetes Mellitus Trial

PI: [name]

Version 5. April 1 2021

randomization. In routine care, HbA1cs are measured approximately every 3-6 months, so we expect only modest missingness, as we have observed also in prior work. Self-reported adherence will be assessed as the proportion of patients who are adherent according to a validated 3-item self-report measure and prior literature from the follow-up questionnaire.³¹ We will also descriptively measure implementation outcomes informed by the RE-AIM framework⁵³, including representativeness of patients in the study, text messaging opt-out rates, any feedback from patients, and rates of pill bottle disconnectedness, which will inform considerations for how to scale the intervention to other settings.

Statistical Analysis

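### Does the 180-day adherence window open before patients on the virtual route have a working pill bottle?

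*Combined protocol and SAP*

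**What the plan says.** - **Outcomes** defines the primary window as "beginning the day after randomization until 180 days after randomization", which is 180 days.
- **Study Procedures** gives the allocation: "the study research assistant will randomize 30 patients to the reinforcement learning arm and 30 patients to usual care". It does not place that step relative to consent, posting of the bottle or the bottle check.
- **1st Virtual Study Visit**: "After this visit, they will be mailed an electronic pill bottle manufactured by Pillsy along with written instructions for setup". The same section then says: "Before beginning follow-up, subjects in both arms will be contacted within 2 business days to review procedures, confirm the functionality of their bottles".
- The next heading, "Optional Check-in", covers receipt and set-up of the posted bottle and repeats the contact without the two-day limit: "Before beginning follow-up, subjects in both arms will be contacted to review procedures, confirm the functionality of their bottles".
- **1st Study Visit** (in-person) hands the bottle over at the visit, so there is no postal gap on that route. The contact before follow-up is worded there as in the virtual visit section.
- **Trial Period** says the bottle uses "electronic date/time stamp technology that is triggered by opening the pill bottle", and that for patients who stay disconnected "study staff may call patients to reconnect their pill bottles at the end of the study".
- **Statistical Analysis** expects no missing primary data and describes the primary comparison as average adherence over the six-month follow-up. Its one rule on non-use is a sensitivity analysis that censors patients who have ceased using the bottle for more than 30 days.
- The figure belonging to **Study Schema** is not reproduced in the text available for this review.

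**The concern.** The outcome clock is tied to randomization, while measurement needs a bottle in the patient's hands. On the virtual route these could be days apart, because posting, set-up and pairing with the phone all come after the first visit. Both contact sentences refer to patients in both arms, which hints that allocation may already have happened by then. A day with no bottle has no openings. If such a day counts as non-adherent, measured adherence falls and the absolute difference between arms shrinks. If it is dropped, neither happens. No readable rule chooses between the two: the 30-day censoring is for patients who stop, not for those who have yet to start. The contact itself has a two-business-day limit with no named starting event in one place, and no limit, under a heading containing the word optional, in the next. Two analysts could therefore use different denominators for the primary endpoint. The virtual route matters because the whole study can be run that way.

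**Working it through.** **1. Order of events in the text.** All three descriptions of the contact (virtual visit, check-in, in-person visit) put it ahead of follow-up. Outcomes describes the primary period as the six months after randomization, and Statistical Analysis calls the period of the primary comparison the six-month follow-up. Read together, these are one period, opening after the bottle has been confirmed to work. The expectation of no missing primary data fits that reading. The text does not state the order outright, and the schema figure may.

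**2. The two descriptions of the contact.** The second omits a limit given in the section just before it. That is not a contradiction. The optional heading can refer to the set-up help offered there, with the contact before follow-up still made for everyone.

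**3. Size if the unfavourable order were true.**

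Inputs from Statistical Analysis: 60 patients (30 per arm), difference 10 points, SD 12.5, alpha 0.05 (taken as two-sided), power 0.8. Assumed, because the documents do not say: mean adherence 75%; start-up delay k of 3, 7 or 14 days; days before bottle use scored as zero; delay unrelated to arm and to true adherence.

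*The plan's own figure.* Standardized effect = 10/12.5 = 0.8. A two-sided t-test at power 0.8 needs 25.5, so 26 per arm (52 in all). Power at 30 per arm is 0.861, and the smallest difference detectable with power 0.8 is 9.20 points. Sixty patients therefore give some room.

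*Uniform delay.* Each patient's average is multiplied by m = (180 − k)/180. Points lost = 75k/180; effect = 10m; SD = 12.5m. The ratio 10m/12.5m stays at 0.8.

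| k (days) | points lost | effect | SD | power |
|---|---|---|---|---|
| 3 | 1.25 | 9.83 | 12.29 | 0.861 |
| 7 | 2.92 | 9.61 | 12.01 | 0.861 |
| 14 | 5.83 | 9.22 | 11.53 | 0.861 |

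*Variable delay.* With mean delay k and delay SD s, put v = (s/180)². Then SD = √[12.5²(m² + v) + 75²v].

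| mean k | s = k/2: SD | power | s = k: SD | power |
|---|---|---|---|---|
| 3 | 12.31 | 0.861 | 12.36 | 0.858 |
| 7 | 12.10 | 0.856 | 12.37 | 0.841 |
| 14 | 11.90 | 0.839 | 12.96 | 0.774 |

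Example, k = 14 and s = 7: m = 166/180 = 0.9222 and v = (7/180)² = 0.001512. SD = √[156.25 × (0.8505 + 0.0015) + 5625 × 0.001512] = √(133.13 + 8.51) = 11.90. Standardized effect = 9.22/11.90 = 0.775, power 0.839.

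*Half the patients in person (no delay), half virtual with delay k.* Effects 9.92, 9.81 and 9.61; SDs 12.41, 12.35 and 12.37; power 0.861, 0.857 and 0.841 for k = 3, 7 and 14.

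*Days left out of the average.* The denominator becomes 180 − k, the effect stays at 10 and power at 0.861.

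**4. Bias between arms.** Equal delays give none. Each day by which one arm started later would move the difference by 75/180 = 0.42 points. The documents give no reason to expect such an imbalance: the posting, set-up and contact steps are the same for both arms.

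**The case for a change.** The strongest case for acting is reproducibility. The outcome is anchored to randomization in so many words, no readable sentence equates that anchor with the start of follow-up, and one added sentence would cost nothing. It is true that the order is inferred and that no rule for days before first use is written down. With a 14-day delay, the two possible denominators would put a patient's average almost 6 points apart.

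Power can also be made to look worse. Holding the SD at 12.5 while shrinking the effect gives 0.850, 0.834 and 0.802 at 3, 7 and 14 days. That calculation does not hold together: a common delay scored as zero rescales every patient's average, so the SD shrinks with the effect. What stands is that variable delays cost some power, and that an average of 14 days with an SD of 14 would take it to 0.774. Nothing in the documents points to delays that long and that scattered.

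A patient who is randomized and never starts a bottle has no assigned value either. That is a separate missing-data question, not one about when the window opens. Days with the bottle in use but disconnected are also separate: the stamp is made on opening, and the end-of-study reconnection call suggests, without proving, that stored openings can be recovered.

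**Conclusion.** No change to the plan follows. This is a detail left unwritten in the readable text, and analysts would fill it sensibly, either by starting the count once the bottle is confirmed or by leaving out days when no bottle was in use. The protocol's own sequence, contact first and follow-up second, supports the harmless reading, and no stated rule is shown to give a wrong result. Under the unfavourable reading the cost is about 0.4 points of measured adherence per day of delay, with no bias between arms if delays are alike. Power is 0.861 for a uniform delay and at least 0.839 for a mean delay of up to 14 days with SD half the mean. It falls below 0.80 only in the extreme case of mean and SD both 14 days. These figures rest on the assumed 75% adherence, the assumed delays, zero scoring, and delay unrelated to arm or true adherence. The missing two-day limit in the second description of the contact is a matter of copy-editing.

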We will report means and frequencies of pre-randomization variables separately by intervention and control arm, comparing these values using absolute standardized differences. The outcomes will be evaluated using intention-to-treat principles among all randomized participants. In the primary analysis, we will evaluate adherence and glycemic control using generalized estimating equations with an identity link function and normally distributed errors. We will also adjust for the block randomized design. We do not expect any missing data for the primary outcome, but may have up to 25% missingness for the glycemic control outcome. If >10% of participants have missing HbA1c data, we will repeat our analyses using multiple imputation. A similar approach will be taken for self-reported adherence, except using a log link function and Poisson distributed errors to generate relative risks of the proportion of adherent patients in the intervention versus control arms. In secondary analyses, we will control for any differences in baseline variables between the arms despite randomization.

As a sensitivity analysis, we will censor patients in the analysis when they have stopped using the electronic pill bottle for >30 days. We will also evaluate the change in HbA1c from baseline until the end of follow-up and differences in self-reported adherence separately for the 3 items that make up the self-reported scale we are using. For glycemic control (HbA1c) and self-reported adherence, we will also conduct complete case analyses. Similarly, subgroup analyses will include stratification by age, sex, race/ethnicity, baseline HbA1c, baseline self-reported adherence, and number of study medications.

Our study should be sufficiently powered to detect clinically meaningful differences in the primary outcome. With 60 subjects, we estimated that we would have the power to detect a 10% difference in average adherence over the 6-month follow-up period between the 2 arms, assuming a standard deviation (SD)=12.5%, power=0.8, and alpha=0.05. With this sample size, we would also be able to detect an HbA1c difference of 1.0% between arms (assuming SD=1.3) and 50% relative difference in self-reported adherence.

Risk and Discomforts

We believe that the risks to participation for subjects are no more than minimal. We do not anticipate the occurrence of any incremental adverse events as a result of patients receiving

Detailed Protocol – Reinforcement Learning in Diabetes Mellitus Trial

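### The HbA1c rule seeks a 6-month value but stops 1 month after randomization; two workable windows fit the text, and the protocol needs to state one

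*Combined protocol and SAP*

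**What the plan says.** The Outcomes section names change in glycemic control, measured by HbA1c, as a secondary outcome. Values come from routine EHR measurements, with no scheduled study draw. The value to be used is the one closest to each patient's "6-month end of follow-up, up to 1 month after", and past the running page header the text continues "randomization. In routine care, HbA1cs are measured approximately every 3-6 months, so we expect only modest missingness". The sentence reads on grammatically across the header, so nothing appears to be lost.

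The same section dates the end of follow-up through the adherence outcome, which runs "beginning the day after randomization until 180 days after randomization".

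The Statistical Analysis section says the trial "may have up to 25% missingness for the glycemic control outcome" and adds: "If >10% of participants have missing HbA1c data, we will repeat our analyses using multiple imputation". Among the sensitivity analyses it lists the "change in HbA1c from baseline until the end of follow-up". No other section gives a date window for HbA1c.

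**The concern.** The target date and the limit contradict each other: a value cannot both represent month 6 and be drawn no later than month 1. The sentence must mean something else, but the protocol does not say what.

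At stake is which laboratory value enters the analysis. Because HbA1c is taken from routine records, the date rule alone decides which result counts for a patient and whether the patient counts as missing. Two analysts working in good faith could build different datasets from the same records. HbA1c is also the only laboratory measure behind the clinical outcomes named in Aim A.

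**Working it through.** **Inputs.** End of follow-up is day 180 (Outcomes). The routine test interval T is 3 to 6 months (Outcomes), with 4.5 months as the midpoint. The missingness ceiling is 25% and the imputation trigger is >10% (Statistical Analysis). There are 60 patients (Subject Selection). One month is taken as 30 days. Assumption, not in the documents: tests are perfectly regular, at random phase relative to randomization, with none skipped and no withdrawals.

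**Formula.** For a window of length L months, the share with no test in it is max(0, 1 - L/T).

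**Step 1: the literal rule.** Day 0 to day 30 ends 180 - 30 = 150 days before the target. With L = 1, missingness is 1 - 1/3 = 67%, 1 - 1/4.5 = 78% and 1 - 1/6 = 83%, against a planned maximum of 25%. This shows only that the literal rule cannot be what was meant.

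**Step 2: the two workable readings.**
- *Slip reading.* Randomization was written for the end of follow-up. The latest date is 180 + 30 = day 210. The earliest is implied: a change from baseline needs a post-randomization value. Window: months 0-7.
- *Look-back reading.* The phrase says how far back the search may go. The earliest date is about day 30. The latest is implied by the end of follow-up. Window: months 1-6.

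**Step 3: how often they disagree.** Let u be the time from month 6 to the first test after it, uniform between 0 and T. The test before that falls at month 6 + u - T.
- If u is at most 1, the slip reading takes the later test, which is the closer one because T is at least 3. The look-back reading cannot use it.
- If u exceeds 1, neither can use the later test. Both take the earlier one, which for T up to 6 lies after month 1.

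The readings therefore differ exactly when u is at most 1, a share of 1/T:

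| T (months) | Share differing | Of 60 patients | Slip reading takes | Look-back reading takes |
|---|---|---|---|---|
| 3 | 33% | 20 | month 6-7 | month 3-4 |
| 4.5 | 22% | 13 | month 6-7 | month 1.5-2.5 |
| 6 | 17% | 10 | month 6-7 | nothing (missing) |

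**Step 4: missingness by window.**

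| Window | L | T = 3 | T = 4.5 | T = 6 |
|---|---|---|---|---|
| Day 0-210 (slip) | 7 | 0% | 0% | 0% |
| Day 30-180 (look-back) | 5 | 0% | 0% | 1 - 5/6 = 17% |
| Day 30-210 | 6 | 0% | 0% | 0% |
| Day 90-210 | 4 | 0% | 11% | 33% |
| Day 150-210 | 2 | 33% | 56% | 67% |

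At 6-monthly testing the look-back reading passes the 10% trigger and the slip reading does not.

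**The case against.** The best defense is that this is a plain drafting error and that the rest of the plan supplies the missing limits. Much of that stands. A reader might infer that no workable reading has both an earliest and a latest date. The documents do not support this: a change from baseline implies a post-randomization value, and the sensitivity analysis runs to the end of follow-up. Each reading then has two limits, one stated and one implied. A look-back with no latest date at all is possible on the words, but it fits poorly with an outcome that runs to the end of follow-up.

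Nor do the missingness statements choose between the readings, since both stay under 25% in this model.

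The model itself is simple. Subject Enrollment describes screening and consent at clinic visits, so tests may cluster around entry and the true disagreement could be larger or smaller. The 0% entries follow from perfectly regular testing and are not forecasts.

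Crossing 10% only adds a repeat analysis with multiple imputation. Complete-case analyses of HbA1c are planned anyway, so the main estimator does not change.

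A reader might also infer a loss of power or a bias from the faulty window. Any power loss at 25% missing follows from the plan's own allowance, whichever window is used. The rule applies equally to both arms, and Study Procedures blinds the analysts.

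What survives is that calling it a typo does not say which correction was meant, and the two candidates select different data.

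**Conclusion.** The point holds as a correction that should be made. The HbA1c rule fails as written, and two different windows can reasonably be read into it. Confidence in the wording defect is high, because it rests on the text alone. The size, 17-33% of patients with a different value or status, is illustrative and rests on the regular-interval, random-phase assumption. The main adherence outcome has a clear window and is unaffected. The documents give no ground for saying that either arm is favored or that the HbA1c comparison cannot be done.

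**What to change.** Before outcome data are extracted, replace the sentence with one that states both limits, for example: *The HbA1c analyzed is the post-randomization result nearest day 180, drawn no earlier than day 30 and no later than day 210; a patient without a result in that range is treated as missing.* Add a tie rule for two equally near results.

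Day 30-210 keeps both limits that the present text suggests. Under the regular-testing assumption it selects the same values as the slip reading, because for T up to 6 months that reading never reaches back before month 1. The sponsor may choose another window, provided that it states both limits and rechecks the 25% figure.

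The cost is one sentence and a date filter in the EHR query, with no new data collection. The trade-off is between relevance and completeness: a wide window admits early values that reflect little of the intervention, while a window of one month either side of day 180 would leave about 33-67% missing, above the plan's ceiling throughout.
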